#### Comparison D:

Hypothesis: Prior exposure to tenofovir gel has no influence on treatment failure rates when a tenofovir-sparing regimen is used.

This comparison involves study populations 1, 2 and 3. The treatment failure rate in the tenofovir-sparing antiretroviral arm of study populations 1 and 3 will be compared to the treatment failure rate in the tenofovir-sparing antiretroviral treatment arm in study population 2.

#### Power

Comparison A: We anticipate that there will be 30 and 30 participants in the two arms.

Comparison B: We anticipate that there will be 20 and 10 participants in the two arms.

Comparison C: We anticipate that there will be 30 and 15 participants in the two arms.

Comparison D: We anticipate that there will be 30 and 15 participants in the two arms.

Power for Comparison A:

A Fisher's exact test with a 0.05 two-sided significance level will have 70% power to detect the difference between a Group 1 proportion, of 0.9 and a Group 2 proportion, of 0.6 when the sample size in the two groups is 30.

Power for Comparison B:

A Fisher's exact test with a 0.05 two-sided significance level will have 25% power to detect the difference between a Group 1 proportion, of 0.9 and a Group 2 proportion, of 0.6 when the sample sizes are 10 and 20, respectively.

Power for Comparison C and D:

A Fisher's exact test with a 0.05 two-sided significance level will have 43% power to detect the difference between a Group 1 proportion, of 0.9 and a Group 2 proportion, of 0.6 when the sample sizes in the two groups are 15 and 30 respectively.

**Table 1:** Statistical power estimates for comparison A based on a range of sample sizes and potential treatment failure rates

Sample size	Proportion with treatment failure			
	0.10 vs 0.30	0.10 vs 0.40	0.05 vs 0.40	0.10 vs 0.50
40/30	44	77	93	94
30/30	37	70	89	91
30/25	34	64	86	86
30/20	28	57	79	82
40/15	28	55	77	79
30/15	22	47	68	72
30/10	15	34	53	56
20/15	18	41	59	67

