**9.3 Data analysis plan**

A Statistical Analysis Plan (SAP) will outline the statistical analyses. The following is a summary of the planned analyses. Any deviations to be made from this summary plan will be documented in the detailed SAP.

A Fisher's exact test will be used to compare the proportion of participants with treatment failure in each of the two arms. We will also do a stratified Mantel Haenszel test where the stratum is the study arm a participant who seroconverted while randomised to tenofovir was in (004, 008 CAPRISA arm or 008 family planning arm). Placebo arm patients will not be stratified.

In addition, treatment failure at 24 and 36 months will be compared between the treatment arms using the same statistical methods as for the primary comparison at 12 months.

All primary analyses will be performed on an intention-to-treat (ITT) basis with additional analyses performed on the per protocol and as treated populations. For the ITT analysis, participants will be analysed according to the study arm, even if the participant did not follow the assigned procedures. The only participants excluded from this primary analysis population will be women with no post-randomisation visit and no data collected. All primary and secondary analyses will be two-sided and will be performed at the 0.05 level of significance.

The analyses of secondary objectives will be described in detail in the SAP.

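### Fisher's exact test uses only about half of the 5% type I error allowed at these group sizes; Boschloo's test would recover power at no cost in participants

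*Protocol*

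**What the plan says.** Section 9.3 of the protocol names the test for the primary outcome: "A Fisher's exact test will be used to compare the proportion of participants with treatment failure in each of the two arms". It adds: "All primary and secondary analyses will be two-sided and will be performed at the 0.05 level of significance". The same method is to be used again at 24 and 36 months, and a stratified Mantel-Haenszel test is planned alongside.

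Section 9.1, under Power, uses the same test with proportions of 0.9 and 0.6:

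- Comparison A, 30 and 30 women: 70%.
- Comparison B, 10 and 20 women: it "will have 25% power to detect the difference".
- Comparisons C and D, 15 and 30 women: it "will have 43% power to detect the difference between a Group 1 proportion, of 0.9 and a Group 2 proportion, of 0.6".

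Table 1 is captioned "Statistical power estimates for comparison A based on a range of sample sizes and potential treatment failure rates". It gives 47% for 30/15 at 0.10 versus 0.40 failure. Neither section says how the two-sided Fisher p-value is formed.

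**The concern.** Fisher's test conditions on the total number of failures. With groups of 10 to 30, few distinct p-values are possible for each total, so the largest attainable error rate at or below 5% is often far below it. The trial then pays in power for protection it did not ask for.

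That matters here because more women cannot simply be enrolled. Section 9.1 derives the sample from the seroconverters expected to need treatment: about 120 gel-exposed women, of whom half give 60, and 60 placebo women, of whom half give 30. No comparison is planned with more than 70% power at 10% versus 40% failure. A test that is valid at 5% and rejects more often with the same women deserves preference, provided that it is fixed before the data are seen.

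**Working it through.** **Inputs.** Two-sided 0.05 (9.1 and 9.3). Proportions 0.9 and 0.6 (9.1), read as success; by symmetry, power is the same for failure of 0.1 and 0.4. Sizes: A 30/30; B 10/20; C and D 15/30, with 0.9 in the smaller group for B, C and D.

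**Formulas.** For x of n1 and y of n2 failures, with m = x + y, the conditional probability of k failures in group 1 is

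P(k) = C(n1,k) C(n2,m−k) / C(n1+n2,m).

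- Equal-tailed p: twice the smaller tail of P.
- Minimum-likelihood p: the sum of all P(k) no larger than P(x).
- Power: the sum, over all tables that reject, of Bin(x; n1, p1) × Bin(y; n2, p2).
- Size: the same sum with p1 = p2, maximised over the common rate.
- Boschloo: use the Fisher p as the statistic and raise the cut-off until the maximum size would pass 5%.

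**Step 1: reproduce the protocol.** The equal-tailed version gives A 70.5%, B 25.4%, and C and D 43.5% (stated 70, 25, 43). It also gives all 32 cells of Table 1 once decimals are dropped.

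**Step 2: 43% against 47%.** The equal-tailed test at 15/30 gives 43.5% with 10% failure in the group of 15, and 47.4% with 10% failure in the group of 30. The text uses the first orientation and the table the second.

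**Step 3: effect of the two-sided p-value.** At 30/30 the two versions agree. At unequal sizes they do not. Take 0 of 15 against 8 of 30:

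- Lower tail: C(30,8)/C(45,8) = 5,852,925/215,553,195 = 0.0272.
- Equal-tailed p: 2 × 0.0272 = 0.054, not significant.
- Minimum-likelihood p: add only the upper tables with smaller probability, k = 6, 7 and 8: (2,177,175 + 193,050 + 6,435)/215,553,195 = 0.0110. The total is 0.038, significant.

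**Step 4: conservatism.** At 30/30 Fisher's size is 0.9% at a common failure rate of 0.10 and 2.6% at 0.30; the maximum over all rates is 2.7%. At 15/30 the maximum is 2.6% (equal-tailed) or 3.3% (minimum-likelihood).

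**Step 5: Boschloo on the minimum-likelihood p.** At 30/30 the cut-off on the Fisher p-value rises from 0.05 to 0.0692. For example, 0 of 30 against 5 of 30 has p = 2 × C(30,5)/C(60,5) = 2 × 142,506/5,461,512 = 0.0522. Fisher does not reject; Boschloo does.

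| Comparison | Stated | Fisher, equal-tailed | Fisher, min.-likelihood | Boschloo (max. size) |
|---|---|---|---|---|
| A, 30/30 | 70% | 70.5% | 70.5% | 74.3% (4.7%) |
| B, 10/20 | 25% | 25.4% | 30.0% | 30.3% (4.1%) |
| C and D, 15/30 | 43% | 43.5% | 52.3% | 57.6% (4.9%) |

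All rows are for 10% versus 40% failure, with 10% in the smaller group where sizes differ.

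**Step 6: split the gain.**

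- A: 74.3 − 70.5 = 3.8 points, all from Boschloo.
- B: 30.0 − 25.4 = 4.6 points from the p-value version and 30.3 − 30.0 = 0.3 from Boschloo.
- C and D: 52.3 − 43.5 = 8.8 points from the p-value version and 57.6 − 52.3 = 5.3 from Boschloo.

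**The case against.** The strongest reply is that Fisher's test is valid, familiar and cautious, so choosing it is not an error. That stands: the point is an improvement, not a correction. The gain is also modest where it counts most, 3.8 points for A, and close to nothing for B beyond the choice of p-value. B, C and D stay weakly powered under every version. Restating the powers changes no sample size.

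A second reply is that the two-sided p-value may be left to the SAP, which 9.3 says will carry the detail and which is not at hand. That also stands. Its absence from the protocol is not a finding; it matters only because the stated unequal-size powers hold for one version and not the other.

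A reader who recomputes C and D with the minimum-likelihood p-value, finds 52%, and sees 43% in the text and 47% in Table 1 might infer wrong arithmetic or a contradiction. The documents support neither. The equal-tailed test is a legitimate two-sided Fisher test and reproduces every stated figure. The 43% and 47% answer two different alternatives. Setting all three side by side mixes two p-value versions with two orientations.

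The caption of Table 1 names Comparison A, for which "We anticipate that there will be 30 and 30 participants in the two arms", yet some rows, such as 30/10 and 40/15, are far from 1:1. The caption also announces a range of sample sizes, so this is editorial.

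**Conclusion.** The concern holds as a choice of method, not as an error. At the planned sizes Fisher's test spends at most 2.7% of the 5% at 30/30, and 2.6% to 3.3% at 15/30. Boschloo's test cannot reject less often than the Fisher p-value on which it is built, because its cut-off is never below 0.05, and its maximum size here is 4.1% to 4.9%.

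Against the stated figures, power at 10% versus 40% failure rises from 70% to about 74% for A, from 25% to about 30% for B, and from 43% to about 58% for C and D. If the analysis would have used the minimum-likelihood Fisher p-value anyway, the real gains are 3.8, 0.3 and 5.3 points.

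These figures assume the planned group sizes, an outcome known for every woman, and 0.9 and 0.6 read as success proportions, with the lower failure rate in the smaller group for B, C and D. For C this is the direction of harm from gel: more failure among the 30 exposed women.

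**What to change.** In 9.3, replace Fisher's exact test by Boschloo's unconditional exact test, two-sided at 0.05 and built on the minimum-likelihood Fisher p-value. Name that construction. Make the change before outcome data are examined.

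In 9.1, restate power for 10% versus 40% failure as about 74% for A, about 30% for B (10 women at 10%, 20 at 40%), and about 58% for C and D (15 women at 10%, 30 at 40%). Rerun Table 1 with the same test, say which group carries the higher failure rate, and widen the caption beyond Comparison A.

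The cost is a less familiar test, some wording and one rerun of the power table; no participants are added. A Barnard-type test is an alternative: it gives 77.9% for A (maximum size 4.7%) but 53.5% for C and D, below Boschloo's 57.6%. Mid-p also gives 77.9% for A, but its maximum size is 5.2%, above the limit.

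If Fisher's test is kept, use one named two-sided p-value for planning and analysis: B 25% and C and D 43% for the equal-tailed version, or 30% and 52% for the minimum-likelihood version. A is 70% under both.

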**9.2 Random assignment**

Enrolled participants will be assigned at random to one of the two study treatment arms in a 1:1 ratio at the time of ART initiation. Randomization will be stratified by study population. The randomization list used to assign individual study participants to one of the two treatment arms will be generated by a randomization statistician who is not otherwise involved in the study. This statistician will use a randomly permuted block design, stratified by site and study population. Two or more pre-specified block sizes will be recorded on a formal randomization request form, but they will not be written in the protocol or communicated to the clinical staff in order to reduce the chance of the clinical staff anticipating the assignment of the next participant. Electronic copies of the randomization schedule and the programs used to generate the randomization schedule will be limited in access and password protected. Paper copies of the randomization schedule will be locked in a secure location at the CAPRISA office, where no unauthorized study staff will have access to them.

The randomisation statistician will provide the site with sealed, opaque randomization envelopes, sequentially labelled by participant identification number (PID). These envelopes will be assigned in sequential order to eligible study participants. Upon opening the envelope the staff member will add his or her name and signature as well as the time and date the envelope was opened. Study arm allocation will be concealed until after a participant is deemed eligible to participate in the study. Once a PID is assigned, the participant will be regarded as enrolled and randomised and the randomization envelope can be opened after the PID is assigned. This is an open label trial and there will be no blinding after the envelope is opened.

**9.3 Data analysis plan**

A Statistical Analysis Plan (SAP) will outline the statistical analyses. The following is a summary of the planned analyses. Any deviations to be made from this summary plan will be documented in the detailed SAP.

A Fisher's exact test will be used to compare the proportion of participants with treatment failure in each of the two arms. We will also do a stratified Mantel Haenszel test where the stratum is the study arm a participant who seroconverted while randomised to tenofovir was in (004, 008 CAPRISA arm or 008 family planning arm). Placebo arm patients will not be stratified.

In addition, treatment failure at 24 and 36 months will be compared between the treatment arms using the same statistical methods as for the primary comparison at 12 months.

All primary analyses will be performed on an intention-to-treat (ITT) basis with additional analyses performed on the per protocol and as treated populations. For the ITT analysis, participants will be analysed according to the study arm, even if the participant did not follow the assigned procedures. The only participants excluded from this primary analysis population will be women with no post-randomisation visit and no data collected. All primary and secondary analyses will be two-sided and will be performed at the 0.05 level of significance.

The analyses of secondary objectives will be described in detail in the SAP.

#### **9.4 Data collection**

Case report forms will be provided for each patient. Participants will be identified by a PID provided by CAPRISA data management centre upon enrolment. The PID is used on all CRFs to identify the participant during the study.

#### **9.5 Data management**

Data will be collected on standardized CRFs which will be developed by the study team. Site study staff will be trained in the correct completion of CRFs. If data entered on the CRFs are taken from an external source (e.g., laboratory reports, patient records), the source documents will be maintained in the participant's medical chart or study file at the site, and will be available for review. The CRFs will be faxed into the database management system which is DataFax version 4.0.0 (or higher) running on SUSE linux V 11. DataFax has optical character recognition (OCR) which will read the check boxes and numerical fields on the CRFs and store them in the study database. Any fields not recognized by the OCR system will be entered manually by the data encoders. Data encoders will verify all data by cross-checking the faxed version to what is entered into the database.

Queries arising during validation of the data will be recorded in quality control (QC) reports sent to the sites on a regular basis. Any queries resulting in a change to the database will be documented and attached to the original CRF. The data management centre staff will perform periodic quality control and validation checks on the data. Database files will be password-protected and access to the files will be limited to authorized study staff members only. All data will be backed up at regular intervals, and backups will be stored in secure areas with limited access.

The original CRFs and related documents will be stored securely at the sites, both during and after the completion of the study. At all sites the forms will be stored in locked cupboards in a secure room with restricted access. Upon completion of the study, the close-out site monitoring visit and finalization of the database for analysis, the original forms will be placed in long term storage. More detail on how the data will be managed will be contained in the study's data management plan.

### **10. Human Subjects Considerations:**

#### **10.1 Regulatory and ethical review**

The study will be conducted under the oversight of the University of KwaZulu-Natal, Nelson R Mandela School of Medicine Biomedical Research Ethics Committee (BREC). The Principal investigator will provide progress reports and all other information required by the ethics committee to conduct its reviews.

#### **10.2 Informed Consent Process**

Written informed consent will be obtained from each study participant prior to enrolment (see Appendix 2). Written informed consent will also be obtained for long-term specimen storage and possible future testing

(see Appendix 2). However, consent for specimen storage is not a pre-condition for study participation. Participants will be provided with a copy of their informed consent forms. Study informed consent forms will describe the purpose of the study, the procedures to be followed, and the risks and benefits of participation. The informed consent forms will also be translated into *isiZulu* and the accuracy of the translation will be verified through independent back-translation. The study consent process will include an assessment of each potential participant's understanding of the study and the risks and benefits of study participation, which are essential for an informed decision. Participants who are not able to demonstrate adequate understanding of key concepts will not be enrolled in the study.

### **10.3 Participant confidentiality**

Every effort will be made to protect participant privacy and confidentiality to the extent permitted by law. Study-related information will be stored securely at the CAPRISA clinical research sites. All participant information will be stored in lockable file cabinets in areas with access limited to study staff. Data collection, process, and administrative forms, laboratory specimens, and other reports will be identified by a coded number only, to maintain participant confidentiality. All records that contain names or other personal identifiers, such as locator forms and informed consent forms, will be stored separately from study records identified by code number. All databases will be secured with password-protected access systems. Forms, lists, logbooks, appointment books, and any other listings that link PID numbers to other identifying information will be stored in a separate, locked file in an area with limited access.

Participant study data, as identified by PID number only, will not be released without the participant's written permission, except as necessary for review and monitoring by:

- Authorized study representatives
- University of KwaZulu-Natal Biomedical Research Ethics Committee
- Study Monitors

### **11. Laboratory Considerations**

The study laboratory plan will include operating procedures for specimen management i.e. specimen collection, chain of custody, handling, labelling, transport; on-site testing; assay procedures; quality assurance procedures and storage procedures.

### **12. Pharmacy**

Study drug will be dispensed from the CAPRISA site pharmacies to study participants. Appropriate accountability of all study product will be maintained at the study pharmacy in accordance with GCP requirements.

### **13. Administrative procedures**

#### **13.1 Protocol compliance**

The study will be conducted in full compliance with the protocol. Amendments to the protocol will be required to follow an SOP which stipulates the levels of approval required prior to submission to regulatory bodies and the steps to be followed prior to implementation of a protocol amendment.

#### **13.2 Protocol violations**

Protocol deviations and violations are broadly defined as any departure from the procedures described in the study protocol. They may impact subject safety, affect the integrity of study data, affect subject's willingness to participate in the study, and/or provide evidence of wilful or knowing misconduct or non-compliance on the part of the site investigator(s) will be documented and reported. Protocol deviations and violations may be identified by any of the study staff or by the study monitor. The procedures for documenting these will be specified in the monitoring plan.

Some examples of protocol violations include:

- Omission or inadequate administration of informed consent
- Inclusion/exclusion errors, including legal age limit
- Missing or incorrectly timed study procedures and assessments

In an emergency, the Investigator may make departures from the protocol to eliminate an apparent immediate hazard for a particular participant. In such a case, he/she will notify the Ethics Committee in writing as soon as possible and document reasons for the violation (unless solely caused by participant non-compliance such as not attending for study visits).

### **13.3 Quality assurance**

The Investigators will allow study monitors to inspect study facilities and documentation (e.g., informed consent forms, clinic and laboratory records, other source documents, CRFs), as well as observe the performance of study procedures. The Investigators will also allow inspection of all study-related documentation by study sponsors. A site visit log will be maintained at the study site to document all visits.

### **14. Use of information and Publications**

Presentation and publication of the results of this study will be governed by CAPRISA's publication policy

## Appendix 1: Schedule of evaluations

	V0	V1	V2	V3	V4	V5	V6	V7	V8	V9	V10
	Scr	Enr	W1	M1	M 3	M 6	M12	M18	M24	M30	M36
CONSENT/ADMIN											
Informed Consent	X	X									
Storage consent		X									
Locator Info	X	X	X	X	X	X	X	X	X	X	X
Risk Reduction		X	X	X	X	X	X	X	X	X	X
Eligibility assessment	X	X									
Randomisation		X									
Adherence support counselling	X	X									
CLINICAL											
Pregnancy test	X	X	X	X	X	X	X	X	X	X	X
FBC	X	X				X	X	X	X	X	X
U+E and Creatinine	X	X				X	X	X	X	X	X
Cholesterol, Trig		X					X		X		X
LFT		X					X		X		X
Fe/B12/Fol		X					X		X		X
Ca/Mg/PO4		X					X		X		X
STI											
RPR		X					X		X		X
HSV & HBV		X					X		X		X
BV		X					X		X		X
GC/CT-VVS		X					X		X		X
VIROLOGY											
RT-PCR/VL		X	X	X	X	X	X	X	X	X	X
Viral isolation		X	X	X	X	X	X	X	X	X	X
Seq (RNA/DNA)		X	X	X	X	X	X	X	X	X	X
Seq mucosal (CVL)		X					X		X		X
IMMUNITY ASSAYS											
	X	X	X	X	X	X	X	X	X	X	X
STORAGE											
Storage-Serum		X	X	X	X	X	X	X	X	X	X
Storage-PBMC		X	X	X	X	X	X	X	X	X	X
MUCOSAL IMMUNOLOGY											
Tear Flo Strips		X					X		X		X
Cytobrush		X					X		X		X
RESISTANCE TESTING											
ARV resistance plasma		X	X	X	X	X	X	X	X	X	X
Tenofovir resistance: Cytobrush		X					X		X		X
Approximate Blood Draw Volumes	13ml	117ml	95ml	95ml	103ml	112ml	117ml	112ml	117ml	112ml	117ml

Note:

1. Enrolment coincides with day of ART initiation
2. These are the study visits. In addition participants will be seen every month for the first 6 months following ART initiation
3. Any test may be performed when clinically indicated

